## **7.5 Subgroup Analyses**

Subgroup analyses for the primary seven-category ordinal outcome (primary efficacy outcome), as well as for the primary safety outcome (Grade 3 and 4 adverse events, SAE or death through Day 7) will be performed to determine whether and how the treatment effect (hIVIG versus placebo) differs qualitatively across various subgroups defined at baseline, and whether there are safety concerns in specific subgroups.

*The protocol denotes the subgroup analysis by the duration of symptoms at study entry as the “key subgroup analysis.” In addition to the analysis by 4 categories of duration of symptoms (<6, 6-7, 8-9, 10-12 days), an analysis based on the upper quartile of symptom duration (e.g., less than or equal to the 75th percentile versus greater than the*

*75th percentile) (2 categories). The upper quartile is 10-12 days (75% of participants will have symptom duration < 10 days). In ACCT-1, a more severely ill target population than studied here, there was no limit to the duration of symptoms and the median was 9 days (25th and 75th percentile, 6 – 12 days). The quartile definitions for duration of symptoms will be determined following the completion of enrollment. For interim analyses, the quartiles will be determined based on interim data. For those with shorter duration of time since symptom onset, the treatment effect is hypothesized to be greater than among participants who have had symptoms for a longer period of time. A global test for heterogeneity of the treatment effect across the symptom duration subgroups will be carried out in 2 ways: 1) by adding the interaction between symptom duration as a continuous variable (1 df test) and the treatment group to the model; and 2) by adding the interaction between categories of symptom duration and the treatment group to the model (3 df test).*

Other important subgroups include subgroups by disease severity, by age, and by pre-existing conditions. *A priori* we have no reason to believe the clinical efficacy or safety of hVIG compared to placebo will be substantially different in relative terms in any of the following subgroups considered. Subgroup analyses for the primary efficacy endpoint and safety endpoint will use the adjusted (cumulative) logistic models described earlier. ORs with 95% CIs comparing the treatment group versus control will be estimated for each subgroup. Global tests for heterogeneity of the treatment effect across subgroups will be carried out by adding the interaction between the subgroup indicator and the treatment group indicator to the model. In case the subgroup was formed by categorizing a continuous variable, the interaction term will be formed between the subgroup indicator and the continuous variable.

Subgroup analyses will not be adjusted for multiple comparisons; they are supportive to the primary endpoint analysis. Subgroup analyses will be interpreted with caution due to limited power and uncontrolled type I error.

*Subgroup analyses will be performed for a number of baseline factors. Unless otherwise stated, continuous outcomes will be summarized in quartiles. The following subgroups will be considered:*

- Age (18-49, 50-59, 60-69, 70+ years)
- Sex at birth (male, female)
- Race/ethnicity (Asian, Black, Latino/Hispanic, White, other)
- BMI [ $<25$ , 25.0-29.9, 30-39, 40+ kg/m^2]
- Presence of chronic medical conditions which had greater than 5% prevalence at baseline (diabetes, hypertension, COPD, asthma, renal impairment)
- Geographic location (U.S.; Europe, UK, or Israel; and Argentina, Indonesia, Japan or Nigeria)
- Upper respiratory SARS-CoV-2 viral load

- Oxygen saturation level
- Dyspnea severity (Modified Borg dyspnea scale)
- Organ/respiratory dysfunction category based on ordinal primary outcome
- NEWS
- *Participants with and without compromised immune function; participants with HIV, an immunosuppressive condition other than HIV, or taking antirejection medication, immune modulators, or biologic treatment for autoimmune disease or cancer will be considered to have compromised immune function.*
- *BMI < 40 and  $\geq 40$  kg/m^2 according to history of diabetes (4 groups)*
- *Hypertension with and without history of other metabolic and vascular co-morbidity (4 groups): i) no hypertension or other metabolic/vascular co-morbidity; ii) hypertension without metabolic/vascular co-morbidity; iii) metabolic/vascular condition without hypertension; and iv) hypertension and a metabolic/vascular co-morbidity. Metabolic/vascular co-morbidities include a history of diabetes, a cerebrovascular event, heart failure, or an MI or acute coronary syndrome.*
- *Number of vascular co-morbidities (0, 1, 2, 3+)*
- *Quartile of Charlson Comorbidity Index (for conditions assessed)*
- *Risk calculator for vaccine prioritization (JHU)*
- *Corticosteroids, overall and in combination with oxygen requirements (ordinal category at baseline)*
- *Use of antiplatelet/anticoagulant therapy (prophylactic heparin, intermediate or therapeutic heparin or other anticoagulant therapy, none)*
- *Quartiles of disease progression risk score (defined using pooled treatment groups with the following baseline predictors of the Day 7 ordinal outcome: age, gender, antigen and antibody level, duration of symptoms, oxygen saturation level, ordinal outcome category at entry, NEWS, and chronic health conditions).*

We will analyse the association between lot potency and the primary outcome for participants assigned active hVIG using a cumulative logistic regression model adjusted for hVIG product and baseline ordinal category. The aim of this analysis will be to determine if the primary outcome varies by range in potency among the various lots of hVIG used.

Additionally, we will explore if the association between lot potency and the primary outcome differs by baseline antibody titre. The potency of each lot will be measured by

Texcell. In addition to the subgroup analyses above, a subgroup analysis by lot potency (by tertiles) will be carried out. Participants in the placebo group will be classified according to the lot potency they would have received had they been randomly assigned to the hVIG group.

If there is a beneficial effect of hVIG compared to placebo, in order to support regulatory claims for each hVIG product used, sensitivity analyses comparing each hVIG product to its matching placebo will be carried out for key efficacy and safety endpoints. First, we will assess the evidence for any difference in effect among the products. A test for heterogeneity of the treatment effect across study products will be carried out by adding the interaction between study product/matching placebo group and the treatment group indicator to the model. In addition to the models for efficacy and safety endpoints described above, we will also test for heterogeneity of the treatment effect across study product/matching placebo group after adjusting for lot potency. In one of the subgroup analyses by hVIG product, the subgroups will be further divided by the potency level of the hVIG lots used for that product (e.g., above and below the median level of lot potency for the product).

Second, we will obtain estimates of the effect for each product using two general approaches. a) We will estimate the effect for each hVIG product using only data from participants receiving that particular product/matching placebo (e.g., separate analyses for each study product). b) We will use multisource exchangeability modelsii (MEMs) to dynamically borrow information from other study products to improve estimation of the efficacy and safety of a single study product. MEMs work by enumerating all possible exchangeability patterns between the data sources (here data from different study products) and obtain a single posterior distribution for the parameter of interest using Bayesian model averaging. The key benefit of this approach is that it can borrow differentially from different study products. Estimates of the effect for each product will be done both adjusting for and not adjusting for lot potency.

These analyses will consider that each hVIG product will be used by a different group of clinical sites (i.e., each comparison will represent a small multi-center trial), and that power will likely be very low for all of the outcomes. Because the hVIG product that each site receives is not randomized, any comparisons of the efficacy among hVIG products should be interpreted cautiously. These analyses are referred to as sensitivity analyses because overall therapeutic efficacy and safety will be based on the pooled analysis of the four hVIG products with placebo.

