Longitudinal random effects models will be used to summarize log-transformed antibody level differences between the hVIG and placebo groups at Days 1, 3, 7 and 28 of follow-up. Baseline antibody levels will be included as a covariate in these

models. For the subset of participants for whom blood is collected at Day 90, antibody levels will be compared.

Subgroup analyses for the primary 7-category ordinal outcome (primary efficacy outcome), as well as for the primary safety outcome (Grade 3 and 4 events, SAE or death through Day 7) will be performed to determine whether the treatment effect (hIVIG versus placebo) differs across baseline-defined subgroups. The key subgroup analysis is by duration of symptoms at study entry. For the subgroup of participants in the lower 3 quartiles, the OR for the primary ordinal outcome at Day 7 is hypothesized to be greater than the overall result and those in the upper quartile (longest duration of symptoms at study entry). The difference in ORs will be compared for those in the lower 3 quartiles versus the upper quartile. In addition, the trend across the four quartiles will be assessed.

The following other baseline-defined subgroups will be considered: age, gender, race/ethnicity, BMI, history of chronic conditions, geographic region, hIVIG product administered, neutralizing antibody level, baseline upper respiratory SARS-CoV-2 viral load, oxygen saturation level, ordinal outcome category at entry, NEWS, dyspnea severity, and a disease progression score. *A priori* we have no reason to believe the clinical efficacy or safety of hIVIG compared to placebo will be substantially different in any of the subgroups considered. These analyses will be approached cautiously because random differences can occur (type 1 error is inflated due to the number of subgroups examined), confounding due to other factors in defining each subgroup is possible, and power is limited. To partially control the inflation of type 1 error and to guide the interpretation of subgroup summaries, an overall test of heterogeneity of treatment effect (treatment by subgroup interaction) will be constructed to assess how strong the evidence is that the treatment effect varies across the baseline subgroups.

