### 1.3 Summary of Changes to SAP

Based on the above information and additional data expected we made the following changes to the SAP:

1. The secondary outcomes of hospitalization status at days 7, 14, and 28, time to discharge, and days alive outside of the hospital at Day 28 will be supplemented with the following additional outcomes: i) time to discharge or being able to independently undertake usual activities with minimal or no

symptoms; ii) time to being able to independently undertake usual activities with minimal or no symptoms (discharge status will be ignored); iii) the binary outcome of hospitalization will also be defined as alive and either discharged from the hospital or being able to independently undertake usual activities with minimal or no symptoms; iv) days alive and able to independently undertake usual activities with minimal or no symptoms at Day 28; and v) days alive and out of the hospital or able to independently undertake usual activities with minimal or no symptoms at Day 28 (whichever lead to greatest time).

Additionally, as a sensitivity analysis for the analysis of time-to-discharge and days outside the hospital we will exclude participants from the 7 sites where no participants were discharged prior to Day 7.

In all of the outcomes related to “discharge”, “discharge” will refer to home, to a rehabilitation center or to a post-acute care facility.

2. The change in NEW score from baseline to Day 3 will not be considered as a secondary outcome because it is only collected for hospitalized participants, and the Day 3 New score is missing for 80 participants (nearly all the participants with missing data had been discharged before Day 3).
3. A key subgroup analysis defined in the protocol is according to duration of symptoms. The primary ordinal outcome will be summarized for the following approximately equal subgroups (<6, 6-7, 8-9, and 10-12 days). The presence of a treatment by subgroup interaction will be estimated in 2 ways, with a 1 degree of freedom (df) test with duration of symptoms included in the ordinal regression model as a continuous variable and with a 3 df test with indicators for categories of duration of symptoms in the regression model.
4. Another important subgroup is by age. The median (25th, 75th percentile) of age is 59 (50, 70) years. Therefore, we will present age in approximate quartiles (<50, 50-59, 60-69, and ≥ 70) years.

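### SAP 7.5: the interaction term for subgroups cut from a continuous variable leaves out treatment, so it cannot test whether the hIVIG effect varies

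*SAP*

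**What the plan says.** SAP section 7.5 sets out global tests for heterogeneity of the treatment effect. The general rule is to test by "adding the interaction between the subgroup indicator and the treatment group indicator to the model". The next sentence gives a special rule for subgroups made by categorizing a continuous variable: "the interaction term will be formed between the subgroup indicator and the continuous variable".

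Elsewhere the documents name treatment:

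- For symptom duration, SAP 7.5 tests by "adding the interaction between symptom duration as a continuous variable (1 df test) and the treatment group to the model", and adds a 3 df test of treatment by duration category. SAP 1.3 item 3 agrees: "The presence of a treatment by subgroup interaction will be estimated in 2 ways".
- For hIVIG product, SAP 7.5 tests by "adding the interaction between study product/matching placebo group and the treatment group indicator to the model".
- Protocol 11.1 says that "an overall test of heterogeneity of treatment effect (treatment by subgroup interaction) will be constructed".

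On a smaller point, SAP 7.5 describes a two-group split of symptom duration in two ways. One, given as an example, is "less than or equal to the 75 th percentile versus greater than the" 75th percentile. The other is "The upper quartile is 10-12 days (75% of participants will have symptom duration < 10 days"). SAP 1.2.3 gives the 75th percentile as 10 days.

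**The concern.** The purpose of the section is to learn whether hIVIG versus placebo differs across baseline subgroups. A product of a variable's categories with the variable itself lets its prognostic slope change from one category to the next. It leaves the treatment effect constant. The resulting p-value would be labelled heterogeneity of the treatment effect but would say nothing about it, and it could be small merely because prognosis is not linear in the variable.

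The special rule follows the general one and is narrower, so read literally it governs the continuous factors in the list. The correct wording for symptom duration and for product applies only to those two. Protocol 11.1 gives the heterogeneity test a real job, which is to limit type 1 error inflation and to guide the reading of the subgroup results. The SAP makes no multiplicity adjustment for subgroups. The rule also covers the primary safety endpoint.

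**Working it through.** The plan states no figure for this test, so there is none to reproduce. The point follows from the model; the simulation only shows its size.

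**Algebra.** Let T be treatment, x the continuous variable and G its category. Other terms that do not involve T are omitted.

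- Written term: logit P(Y ≤ k) = α_k + βT + γ_G + δx + θ_G·x. Setting T = 1 and T = 0 and subtracting gives β for every x and G. The hIVIG log OR is constant whatever θ is, so testing θ = 0 tests prognostic shape.
- Treatment by continuous: logit P(Y ≤ k) = α_k + βT + δx + λTx. The difference is β + λx. Testing λ = 0 tests heterogeneity.

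**Simulation inputs from the documents.** n = 579 (SAP 4), 1:1 allocation, OR 1.61 and the Table 1 placebo distribution (SAP 1.4), baseline oxygen shares 28/34/28/10% (SAP 1.2.3), product shares 155/153/146/139 of 593 (SAP 1.2.4), and two-sided 0.05 (SAP 7). Applying OR 1.61 to the placebo column gives 7.8, 57.6, 15.1, 10.6, 4.2, 4.0 and 0.6%, which is the hIVIG column of Table 1.

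**Assumptions.** A normal covariate with slope -0.3 log-odds per SD, cut in quartiles; baseline category effects 0.8/0/-0.8/-1.6; and the interaction and curvature sizes shown below. Baseline category and product enter as proportional effects. The SAP's interactions with the six cutoffs are left out as a simplification.

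Likelihood-ratio tests at 0.05, 2000 trials per row, Monte Carlo standard error at most √(0.25/2000) = 1.1 points. Percentage of trials rejecting:

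| Truth | Written term (3 df) | Treatment × continuous (1 df) | Treatment × quartile (3 df) |
|---|---|---|---|
| No interaction, linear prognosis | 5.5 | 5.9 | 6.0 |
| Interaction 0.25 per SD | 5.6 | 35.4 | 21.7 |
| Interaction 0.5 per SD | 5.7 | 86.4 | 66.6 |
| No interaction, curvature -0.15 per SD² | 38.6 | 6.1 | 5.4 |
| No interaction, curvature -0.3 per SD² | 93.4 | 7.2 | 4.6 |

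A simpler simulation agrees. It used logistic regression on the two best categories with 54% in placebo (Table 1), n = 579, an assumed slope of -0.4, and 2000 trials per setting. At interactions of 0 / 0.3 / 0.5 per SD, the written term rejected in 6 / 6 / 6%, treatment × continuous in 6 / 40 / 80%, and treatment × quartile in 6 / 23 / 57%.

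**Symptom-duration split.** With a 75th percentile of 10 days, a participant at day 10 is at or below it and falls in the lower group. Under the other description, and under the fixed categories <6, 6-7, 8-9 and 10-12 in SAP 1.3 item 3, the same participant is in the upper group. A quarter of 579 is 0.25 × 579 = 144.75, about 145. The number at exactly day 10 is not given. If it is one third to two thirds of 145 (an assumption), 48 to 97 participants change group, and the upper group falls from about 145 to between 97 and 48.

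**The case against.** The strongest reply is that this is a slip whose intent is easy to recover. The sentence directly follows one that defines the test through the treatment indicator, the symptom-duration rule shows the intended construction, and nobody set out to test prognostic shape. Most of that stands, and the wording for symptom duration and product is better read as evidence of intent than as contradiction, since each has its own specification. The direct conflicts are with the preceding sentence and Protocol 11.1. But an analysis plan should be programmable without guessing, and no passage restores the treatment factor for the other continuous variables.

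It is also fair that zero power follows by construction, so the interaction rows illustrate rather than prove, and that all effect sizes are assumed. The curvature rows add something: the written term does not merely miss heterogeneity, it can signal heterogeneity that is absent.

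The consequence is small. SAP 7.5 calls the subgroup analyses supportive and urges caution. That limits the weight of the point without removing it.

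On the split, the percentile version is only an example, and the fixed categories make <10 versus 10-12 days the likely intent. That part is a clarification, and the main point does not depend on it.

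**Conclusion.** The concern holds. As written, the rule in SAP 7.5 for subgroups cut from a continuous variable cannot detect variation in the hIVIG effect. Its rejection rate stays at the null level (5.6% and 5.7% against 5.5%) in settings where treatment by continuous variable rejects in 35.4% and 86.4%. It rejects in 38.6% or 93.4% of trials under curved prognosis with no interaction. The rates depend on the assumed effects and the simplified model; the absence of treatment from the term does not.

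The main point reaches only the supportive heterogeneity tests for continuous factors such as age, BMI, viral load, oxygen saturation, NEWS and the risk score, for the primary efficacy and safety endpoints. The primary analysis, the subgroup-specific ORs for the listed subgroups, the tests for purely categorical subgroups, and the 1 df and 3 df symptom-duration tests are unaffected. The split ambiguity touches only the OR in the lower three quartiles of symptom duration (SAP 1.4) and its comparison with the upper quartile (Protocol 11.1). It should be corrected, but it does not threaten the trial's main conclusion.

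**What to change.** In the SAP 7.5 sentence, write treatment group indicator in place of subgroup indicator, so that the test is treatment by continuous variable (1 df), and say that the continuous main effect is in the model.

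Optionally, report the treatment by category test beside it, as the SAP already does for symptom duration. In the simulation the 1 df test had more power for a linear trend and the category test was less sensitive to curved prognosis.

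For symptom duration, replace the whole percentile example with <10 versus 10-12 days. Removing only the word that marks it as an example would turn the conflicting cut into a rule.

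The cost is one phrase, a note on the main effect and one replaced parenthesis, plus a sentence if the second test is added. No new data are needed and the primary analysis does not change.

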#### **5.4 Distribution of Anti-Coronavirus hIVIG to Clinical Sites**

It is critical to establish whether Anti-Coronavirus hIVIG is safe and effective as rapidly as possible. To accomplish this, hIVIG will be manufactured for use in this trial by 3 different groups. Four hIVIG products, two produced by an Alliance of several companies including Takeda Pharmaceuticals and CSL Behring, and one each produced by Emergent BioSolutions and Grifols Shared Services North America, Inc., will be used. No single group can prepare sufficient quantity of hIVIG product to rapidly complete this trial. Thus, for practical reasons, the primary analysis (see Section 11.1) which compares the hIVIG and placebo groups on Day 7 for the primary ordinal endpoint will pool the outcome results for the 4 different hIVIG products and matching placebos.

[figure not shown]
To simplify logistics related to the supply of hIVIG to clinical sites and to take advantage of the randomization, which is stratified by site pharmacy, the same hIVIG product will be provided to a given site pharmacy for the duration of the trial to the extent possible. This is illustrated in Figure 2 with an example that assumes that there are 24 site pharmacies and the supply of each of hIVIG products will be the same.

The site pharmacy allocation of hIVIG will take into account estimates of the number of participant doses each manufacturer will provide and estimates of the number of participants to be enrolled by sites using each site pharmacy (i.e., it may not be an equal number of site pharmacies or participants for each hIVIG product).

It is likely that the hIVIG provided by each manufacturer will be from more than one lot during the study. For each individual participant, all hIVIG vials used will come from the same lot. This plan for distributing the hIVIG will simplify the tracking of lots used by each site pharmacy. This plan also simplifies the pharmacy plans prepared for each site pharmacy.

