In addition to these subgroup analyses, a subgroup analysis by lot potency will be carried out. The aim of this analysis will be to determine if the primary outcome varies by range in potency among the various lots of hIVIG used. The potency of each lot will be measured by a central laboratory. Participants in the placebo group will be classified according the lot potency they would have received had they been randomly assigned to the hIVIG group. The methods used for this subgroup analysis will be as described above.

If there is a beneficial effect of hIVIG compared to placebo, in order to support regulatory claims for each hIVIG product used, sensitivity analyses comparing each hIVIG product to its matched placebo will be carried out for key efficacy and safety endpoints. These analyses will consider that each hIVIG product will be used by a different group of clinical sites (i.e., each comparison will represent a small multi-center trial), and that power will likely be very low for all of the outcomes. These analyses are referred to as sensitivity analyses because overall therapeutic efficacy and safety will be based on the pooled analysis of the four hIVIG products with placebo.

If the hIVIG and placebo groups differ for the primary ordinal outcome at Day 7, the extent to which a favourable treatment difference for hIVIG can be explained by antibody levels measured at baseline and Days 1, 3, 7, and 28 of follow-up will be investigated.

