### **Randomization**

Randomization will be stratified by site pharmacy (clinical sites may share a pharmacy). Participants will be randomized (1:1) to a single infusion of hIVIG + SOC or placebo + SOC on the day of randomization (Day 0).

Hyperimmune IVIG will be manufactured by four companies; to simplify logistics related to the supply of hIVIG to clinical sites and to take advantage of the randomization, which is stratified by site pharmacy, the same hIVIG product will be provided to a given site pharmacy for the duration of the trial to the extent possible. This is illustrated in Figure 1 with an example that assumes that there are 24 site pharmacies and the supply of each of hIVIG products will be the same.

Within each stratum permuted block randomization will be used to generate treatment assignments.

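### One lot-potency model in SAP 7.5 compares non-randomised lots within the hIVIG arm, so pharmacy differences could appear as a potency association; potency conclusions should rest on a two-arm interaction

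*SAP*

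**What the plan says.** SAP 7.5 begins its lot-potency plan with a model confined to the treated arm: "We will analyse the association between lot potency and the primary outcome for participants assigned active" hIVIG, "using a cumulative logistic regression model adjusted for hVIG product and baseline ordinal category". No term for pharmacy, site, region or calendar time is named, and no allowance for clustering. The SAP then adds that "a subgroup analysis by lot potency (by tertiles) will be carried out". In that second analysis both arms are used: "Participants in the placebo group will be classified according to the lot potency they would have received" had they been allocated to hIVIG.

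Protocol 11.1 has only the two-arm version. Its aim is to "determine if the primary outcome varies by range in potency among the various lots" of hIVIG used, and it continues: "Participants in the placebo group will be classified according the lot potency they would have received had they been randomly assigned" to hIVIG. The SAP attaches that same aim to the hIVIG-only model.

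On supply, SAP 1.4 (Randomization) says that "the same hIVIG product will be provided to a given site pharmacy for the duration of the trial to the extent possible". On lots, Protocol 5.4 says that more than one lot per manufacturer is likely, that each participant's vials come from one lot, and that "This plan for distributing the hIVIG will simplify the tracking of lots used by each site pharmacy". SAP 1.2.4 gives 44 lots (5, 3, 22 and 14 by product) at 47 pharmacies (11, 11, 11 and 14) for 593 participants (155, 153, 146 and 139).

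Two other parts of SAP 7.5 bear on this. Where a subgroup comes from cutting a continuous variable, the interaction is said to be formed between the subgroup indicator and that variable; treatment is not mentioned. And, among analyses to be done if hIVIG shows benefit, one divides each product's participants by the potency of its lots.

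**The concern.** Potency is a property of a lot, and no one was randomised to a lot. Within the hIVIG arm, a potency slope is an observational comparison between the groups who happened to receive different lots. Adjusting for product removes differences between products, but not differences between pharmacies that used the same product. If lots of one product went to different pharmacies, and those pharmacies differ in case mix or in practice beyond what the entry category captures, the slope absorbs the difference. The ordinary standard error treats participants as independent and can be too small.

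Randomisation was stratified by pharmacy, so placebo participants at the same pharmacy are the natural control. A pharmacy effect common to both arms cancels in a treatment-by-potency contrast. The SAP already plans to give placebo participants a lot potency, yet it attaches the stated aim to the model that leaves them out.

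What is at stake is any statement that outcome does, or does not, vary with potency.

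**Working it through.** **Anchor to the plan's own figures.** The documents give no power or error rate for the lot-potency analysis. The nearest figure is the primary sample size of 494. The Whitehead formula is N = 12(z₀.₉₇₅ + z₀.₈₀)² / [(ln OR)²(1 − Σp̄³)]. With OR 1.61 and Table 1 (hIVIG column rescaled, since it is printed as summing to 99.9), 12 × 7.849 = 94.19, (ln 1.61)² = 0.2268 and 1 − Σp̄³ = 0.8413. Then N = 94.19 / (0.2268 × 0.8413) = 493.6, which reproduces 494. This confirms the outcome distribution used below and says nothing about potency.

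**Inputs from the documents.** Participants, pharmacies and lots by product are from SAP 1.2.4. Lot potency has median 1220 and quartiles 893 and 1442 IU/mL. Taken as log-normal, its SD is ln(1442/893) / (2 × 0.6745) = 0.479/1.349 = 0.355. The entry mix of 28/34/28/10% is from SAP 1.2.3. Allocation is 1:1 within pharmacy, and tests are two-sided at 0.05.

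**Assumptions not in the documents.** Between-pharmacy SD σ of 0 to 1.0 on the log-odds scale; the share of participants whose lot is determined by their pharmacy (100, 50 or 0%); uneven pharmacy sizes; and the strength of the entry-category effect. The latent intraclass correlation is σ²/(σ² + 3.29).

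**Simulation under the null.** There was no treatment or potency effect, with 800 trials per setting. The simulation error near 5% is √(0.05 × 0.95/800) = 0.8 points. The table shows the percentage of trials rejecting at |Z| > 1.96.

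| σ | ICC | hIVIG only, lot fixed by pharmacy | hIVIG only, half linked | hIVIG only, no link |
|---|---|---|---|---|
| 0 | 0 | 5.5 | 7.8 | 5.5 |
| 0.25 | 0.02 | 5.9 | 6.5 | 6.0 |
| 0.5 | 0.07 | 10.2 | 6.9 | 5.5 |
| 0.75 | 0.15 | 17.4 | 8.9 | 4.5 |
| 1.0 | 0.23 | 20.8 | 9.5 | 4.9 |

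The two-arm treatment-by-log-potency test rejected in 3.4 to 6.0% across all 15 settings. The hIVIG-only model with a pharmacy-clustered variance rejected in 5.2 to 9.6%, so with so few lots clustering alone does not bring it back to 5%.

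Two cautions apply. At σ = 0 linkage cannot matter, so the 7.8% in the half-linked column is noise or a small-sample feature, and that column shows at most a modest rise. The two-arm model simulated here had product as a main effect but no treatment-by-product term.

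**Second simulation.** A smaller set, with 250 trials per setting and 1 to 2 lots per pharmacy assumed, gave 10 to 18% for the hIVIG-only model at σ = 0.5 to 0.7, 5 to 6% at σ = 0.3, and 4 to 6% for the two-arm test. Its simulation error is 1.4 points at 5% and 2.4 points at 18%. At σ = 0.5 to 0.7 the empirical SD of the hIVIG-only slope was 1.17 to 1.48 times the model standard error. That makes the standard error 1 − 1/1.17 = 15% to 1 − 1/1.48 = 32% too small. At σ = 0.3 the ratio was about 1.03.

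**Price of the two-arm test.** The interaction is a difference of two slopes from arms of similar size, so its standard error is about √2 = 1.4 times the single-arm model standard error.

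**The case against.** The strongest reply is that the controlled analysis is already planned. That is largely right. A reader might infer from the quoted sentence that potency is examined only in the hIVIG arm. The documents do not support this: SAP 7.5 also plans the two-arm tertile subgroup, Protocol 11.1 plans the two-arm version alone, and SAP 7.5 adds a within-product split by potency if there is benefit. The SAP's rule for continuous variables may also be meant to give a treatment-by-potency term, as it does explicitly for symptom duration.

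What remains is narrower. The tertiles pool four products. Product indicators enter those models, but no treatment-by-product term is specified, so a potency gradient in the treatment effect could reflect product. The rule for continuous variables, as written, does not name treatment. The within-product split depends on a beneficial result.

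The second reply is that linkage is assumed. This also stands. A reader might infer that lots were tied to pharmacies, but the documents tie product to pharmacy, and for lots they mention only tracking. Three lots across 11 pharmacies must have been shared, at once or in turn. With 22 lots across 11 pharmacies, at most two lots per pharmacy is possible only if every pharmacy used exactly two and shared none. More lots per pharmacy would weaken the linkage.

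Third, a reader might take this model to be the evidence on which dose optimisation depends. Protocol 8.1.2 rests that on neutralizing titers and clinical outcome; product potencies are only listed as something to be measured.

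Finally, SAP 7.5 already describes subgroup analyses as supportive, unadjusted and to be read with caution. That limits the consequence. However, its specific warning about non-randomised comparison concerns products, not lots.

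**Conclusion.** The point holds for one of the planned lot-potency analyses. The hIVIG-only model is a non-randomised comparison of lots, and the SAP gives it the aim that the protocol attached to the placebo-classified analysis. It can report pharmacy differences as a potency association, and its intervals can be too narrow, if lots followed pharmacies within a product and pharmacies differed in outcome. Neither condition can be settled from the documents.

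The false-positive rate is about 10 to 20% under full linkage with a pharmacy SD of 0.5 to 1.0, about 6.5 to 9.5% with half of participants linked (SD 0.25 to 1.0), and near 5% with no linkage. Under full linkage it stays at about 5 to 6% when the SD is 0.3 or less. It would therefore go too far to say that the intervals are too narrow. A need for pharmacy-clustered variance in the two-arm model was not shown either, since that test kept its level without it.

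This is a cheap improvement to a supportive analysis. The pooled primary comparison is unaffected.

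**What to change.** Amend SAP 7.5 as follows.

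1. State that any conclusion about potency rests on a two-arm cumulative logistic model with treatment, log lot potency (placebo participants coded by the lot they would have been given, as already planned), treatment by log potency, product, treatment by product, and entry category. The treatment-by-log-potency coefficient is the test.
2. Correct the rule for categorised continuous variables so that the interaction is between treatment and the continuous variable.
3. Keep the hIVIG-only model, labelled descriptive and non-randomised, with no conclusion drawn from its p-value.
4. Report a table of participants by lot and pharmacy, so that readers can judge how far lots followed pharmacies.

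Pharmacy-clustered variance in the two-arm model is optional.

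The cost is wording; no new data are needed. The statistical price is a standard error about 1.4 times that of the hIVIG-only model, hence less power to detect a real potency gradient. The treatment-by-product term may widen the interval further if potency differs mainly between products.
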